12.4 Medical Monitoring

It is the responsibility of the Principal Investigator to oversee the safety of the study at his/her site. This safety monitoring will include careful assessment and appropriate reporting of adverse events as noted above, as well as the construction and implementation of a site data and safety-monitoring plan, medical monitoring will include a regular assessment of the number and type of serious adverse events.

13 Data Handling and Record Keeping

13.1 Confidentiality

Information about study subjects will be kept confidential and managed according to the requirements of the Health Insurance Portability and Accountability Act of 1996 (HIPAA). Those regulations require a signed subject authorization informing the subject of the following:

- What protected health information (PHI) will be collected from subjects in this study
- Who will have access to that information and why
- Who will use or disclose that information
- The rights of a research subject to revoke their authorization for use of their PHI.

In the event that the subject revokes authorization to collect or use PHI, the investigator, by regulation, retains the ability to use all information collected prior to the revocation of subject authorization. For subjects that have revoked authorization to collect or use PHI, attempts should be made to obtain permission to collect at least vital status (long term survival status that the subject is alive) at the end of their scheduled study period.

13.2 Source Documents

Source data is all information, original records of clinical findings, observations, or other activities in a clinical trial necessary for the reconstruction and evaluation of the trial. Source data are contained in source documents. Examples of these original documents and data records include hospital records and any forms completed specifically for this study.

13.3 Case Report Forms

CRFs will be developed to collect study-specific data points.

13.4 Data Management

Study data to be collected and managed using EHR and transcribed into electronic CRFs in an electronic data capture system that is a secure, web-based application designed to support data capture for research studies.

13.5 Data Processing

All study data will be stored within the electronic data capture system. The principal investigator will be responsible for overseeing the analysis of the data. De-identified data will be shared with the study sponsor.

13.6 Data Security and Confidentiality

All source documents including clinical findings, observations or other activities will be stored in an electronic database and overseen by the Investigator. Access to the database will be limited to the Principal Investigator, Investigators, Study Team members, and Statistician.

13.7 Data Quality Assurance

Once the study is completed, the Principal Investigator will randomly select 1 participant and compare the data documented in the EHR with what is entered into the electronic database. If there is any discrepancy, the Principal Investigator and/or Investigators will cross-reference all patients to ensure accuracy.

13.8 Data Clarification Process

For any data query, the site's Principal Investigator and Sub-Investigators will meet to clarify the data queried and make corrections based on consensus.

13.9 Records Retention

The site's Principal Investigator will maintain records and essential documents related to the conduct of the study. These will include subject case histories and regulatory documents. The site's Principal Investigator will retain the specified records and reports.

14 Study Monitoring, Auditing, and Inspecting

14.1 Study Monitoring Plan

The site's Principal Investigator will allocate adequate time for such monitoring activities. The Principal Investigator will also ensure that the compliance or quality assurance reviewer is given access to all the study-related documents.

14.2 Auditing and Inspecting

The investigator will permit study-related monitoring, audits, and inspections by the IRB, the sponsor, and government regulatory agencies, of all study related documents (e.g. source documents, regulatory documents, data collection instruments, study data etc.). Participation as a Principal Investigator or Sub-Investigator in this study implies acceptance of potential inspection by government regulatory authorities and applicable compliance offices.

15 Ethical Considerations

This study is to be conducted according to United States government regulations and Institutional research policies and procedures and the requirements of the Regulation (EU) 2017/745 Chapter VI and Annex XV.

This protocol and any amendments will be submitted to a properly constituted local Institutional Review Board (IRB)/EC, in agreement with local legal prescriptions, for formal approval of the study. The decision of the IRB concerning the conduct of the study will be made in writing to the site's Principal Investigator before commencement of this study.

All subjects for this study will be provided a consent form describing this study and providing sufficient information for subjects to make an informed decision about their participation in this study. This consent form will be submitted with the protocol for review and approval by the IRB/EC for the study. The formal consent of a subject, using the Approved IRB/EC consent form, must be obtained before that subject undergoes any study procedure. The consent form must be signed by the subject and the individual obtaining the informed consent.

16 Study Finances

161 Funding Source

Single Pass, Inc. is the funding sponsor of this study.

162 Conflict of Interest

Any study team member who has a conflict of interest with this study (patent ownership, royalties, or financial gain greater than the minimum allowable by their institution, etc.) will have the conflict reviewed by a properly constituted Conflict of Interest Committee with a Committee-sanctioned conflict management plan that has been reviewed and approved by the study site's Principal Investigator prior to participation in this study.

163 Subject Stipends or Payments

Subjects may receive a stipend payment for participation, but only within a fair and reasonable amount.

17 Publication Plan

Attachment A: Kronos Scoring Criteria

Attribute	Score				
	1 Unacceptable	2 Unsatisfactory	3 Acceptable	4 Good	5 Excellent
Device Condition (Visual Inspection)	Device was unable to prepare. Device was unable to connect for use	Device was difficult to prepare. Device was difficult to connect to fittings with insecure connection	Device was easy to prepare. Device was able to connect to fittings with some issues	Device was easy to prepare. Device was able to connect to fittings with slight issue	Device was easy to prepare. Device was able to connect to fittings without issue
Maneuverability to Target Tissue	Device was unable to maneuver to target tissue	Device was difficult to maneuver to target tissue	Device was able to maneuver to target tissue with some issue	Device was able to maneuver to target tissue with slight issue	Device was able to maneuver to target tissue without issue
Device Performance (Blood Control)	Device was unable to cease blood at target vessel	Device was able to cease blood at target vessel with great difficulty	Device was able to cease blood at target vessel with some issue	Device was able to cease blood at target vessel with slight issue	Device was able to cease blood at target vessel without issue
Compatibility with Guide Needle	Device was unable to track through guide needle	Device was able to track through guide needle with a lot of friction	Device was able to track through guide needle with some friction	Device was able to track through guide needle with slight friction	Device was able to track through guide needle without friction
Withdrawal Force	Device was unable to be removed from target vessel	Device was able to be removed from target vessel with a lot of friction	Device was able to be removed from target vessel with some friction	Device was able to be removed from target vessel with slight friction	Device was able to be removed from target vessel without friction

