IB	Investigator's Brochure
IRB	Institutional Review Board
Non-UPIRTSO	Non-Unanticipated Problems Involving Risk to Subjects or Others
PHI	Protected Health Information
PI	Principal Investigator
SAE	Serious Adverse Event/Serious Adverse Experience
SOP	Standard Operating Procedure
UPIRTSO	Unanticipated Problems Involving Risk to Subjects or Others

3 Study Summary

Title	Feasibility Study of the Kronos Electrocautery Device
Protocol Name	Kronos Study
Protocol Number	SP-01, Version 1.0
Phase	N/A
Methodology	Pilot Study, Non-Randomized
Overall Study Duration (Estimated)	4 months
Subject Participation Duration (Estimated)	14 Days post procedure
Number of Sites	Up to 5
Objectives	The primary objective for this study is to assess safety and performance of the Kronos Electrocautery Device for electrocautery procedures following coaxial biopsy procedures on areas that include, but are not limited to, liver, kidney, lungs, breasts, soft tissue, etc.
Intended Purpose	The Kronos Electrocautery Device is intended to be used in electrocautery procedures to control bleeding by use of electrical current to heat the device probe tip that is applied directly to the target tissue area of treatment.
Study Design	Prospective, multicenter, single arm study with consecutive, eligible subject enrollment at each site. Patients who require a coaxial biopsy procedures on areas that include, but are not limited to, liver, kidney, lungs, breasts, soft tissue, etc., will be eligible to participate in this study.
Number of Subjects	Up to 30 patients
Primary Endpoint	Assess rate of successful electrocautery procedure in absence of procedure related Adverse Events
Inclusion Criteria	
 1. Patients undergoing a scheduled elective coaxial biopsy procedures on areas that include, but are not limited to, liver, kidney, lungs, breasts, soft tissue, etc., 2. Patients have signed an informed consent 3. Patients who are \geq 18 years of age.

Exclusion Criteria	
1. Patients with known bleeding disorder2. Significant congenital anomaly or medical problem that in the opinion of the investigator would preclude enrollment in this study.3. Women of childbearing potential who are pregnant, lactating, or planning to become pregnant during the course of the clinical investigation.4. Active systemic infection or sepsis.
Study Device	Kronos Electrosurgical Device

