10.2 Visit 2 (Treatment – Day of Biopsy procedure)

1. Ultrasound guided percutaneous biopsy will be performed as per standard of care
2. Placement of the desired core biopsy needle and guide needle will be as per standard of care
3. The needle will be removed, leaving the guide needle in place.
4. Biopsy forceps will be advanced through the guide needle to obtain the tissue
5. The biopsy forceps will be removed with the tissue
6. Remove Kronos Electrosurgery Device from packaging and visually inspect. Record Device Condition score per Attachment 1 – Kronos Scoring Criteria
7. Using the current Instruction for Use (IFU), the Kronos Electrosurgery Device will be advanced to a predetermined length (recorded) to ensure that it protrudes into the biopsy track. Record Maneuverability to Target Tissue score per Attachment 1 – Kronos Scoring Criteria. If Guide needle was used, record Compatibility with guide needle score per Attachment 1 – Kronos Scoring Criteria
8. The Kronos Electrosurgery Device will be activated, and the device and guide needle will

be withdrawn simultaneously at controlled speed. The total time of withdrawal (recorded). Record Withdrawal Force score per Attachment 1 – Kronos Scoring Criteria

9. Any blood or fluids from the access site will be soaked up with a dry gauze without placing any pressure on the access site.
10. Blood or other fluids will be collected for a minimum of five minutes, or until all bleeding has stopped (if applicable). The gauze will be weighed (recorded) to estimate the blood loss with results. Record Device Performance (Blood control) score per Attachment 1 – Kronos Scoring Criteria.
11. This procedure will be performed a single time, on areas that include, but are not limited to, liver, kidney, lungs, breasts, soft tissue, etc.,.. The biopsy procedure is being performed as a standard of care, which may require multiple passes.

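### The Blood Control score is required in every patient but has no level for a tract that was not bleeding, and bleeding before activation is not recorded, so the score cannot be read as bleeding control

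*Combined protocol and SAP*

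**What the plan says.** Section 10.2 sets the order of events. In step 7 the device "will be advanced to a predetermined length (recorded) to ensure that it protrudes into the biopsy track". In step 8, "The Kronos Electrosurgery Device will be activated, and the device and guide needle will" be withdrawn together. Blood is first dealt with after that. Step 9 reads "Any blood or fluids from the access site will be soaked up with a dry gauze", and step 10 reads "Blood or other fluids will be collected for a minimum of five minutes, or until all bleeding has stopped (if applicable"). The gauze is then weighed, and step 10 ends with the instruction "Record Device Performance (Blood control) score per Attachment 1".

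That instruction carries no condition. Step 7 shows how the protocol writes a conditional score: "If Guide needle was used, record Compatibility with guide needle score per Attachment 1".

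The scale is in Attachment A, which section 10.2 calls Attachment 1. Level 1 of Blood Control is for a device that could not stop the blood. Levels 2 to 5 are for a device that stopped it with decreasing difficulty, ending at "Device was able to cease blood at target vessel without issue". There is no level for absence of bleeding and no not-applicable option.

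The Study Summary states: "The primary objective for this study is to assess safety and performance of the Kronos Electrocautery Device". Blood Control is the only one of the five attributes labelled as device performance. The primary and secondary outcomes in section 7.4 do not name it. The Study Summary says that all reporting is descriptive.

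**The concern.** A rating of how well bleeding was stopped has meaning only where there was bleeding to stop. The protocol asks for the rating in everyone, gives no level for the patient with nothing to stop, and does not record which patients those were. Stopped bleeding and absent bleeding then fall into the same score.

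Two things are at stake. A rater facing a dry tract may well choose the top level, since nothing went wrong, and that would make performance look better than it was where bleeding occurred. Others may leave a blank, so with up to 5 sites the same clinical picture can be coded in different ways. In addition, bleeding status before activation cannot be reconstructed once the procedure is over, so the problem cannot be repaired at analysis.

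**Working it through.** **Text check.** The plan gives no target, power or expected value for this score, so there is no figure to reproduce. The check is what section 10.2 records, and when.

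- Steps 1 to 5 (biopsy): no recorded item.
- Steps 6 to 8 (inspection, advancement, activation and withdrawal): device condition, advanced length, maneuverability, guide-needle compatibility, withdrawal time and withdrawal force.
- Steps 9 and 10 (after withdrawal): gauze weight and the Blood Control score.

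Nothing before activation concerns bleeding, and the schedule in section 10.3 adds no such item. Gauze weight does not fill the gap. It is taken after treatment, and the gauze collects other fluids as well as blood.

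**Size, as an illustration only.** The inputs are n = 30 (section 11.1), or n = 20 for the minimum accrual in section 8.3. Two further inputs are assumed, because the documents do not give them: d, the share of tracts dry before and after, and p, the share of bleeding tracts that earn a 5. For simplicity, no tract that was dry beforehand bleeds later.

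- If dry tracts are scored 5, the share scoring 5 is d + (1 − d)p.
- If dry tracts are left blank, the share scoring 5 is p, on n(1 − d) patients.
- The difference is d(1 − p). It is zero if no tract is dry or if every bleeding tract scores 5.

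| Dry of 30 | p | Dry scored 5 | Dry left blank | Difference (points) |
|---|---|---|---|---|
| 3 | 2/3 | (3+18)/30 = 70.0% | 18/27 = 66.7% | +3.3 |
| 3 | 1/3 | (3+9)/30 = 40.0% | 9/27 = 33.3% | +6.7 |
| 15 | 2/3 | (15+10)/30 = 83.3% | 10/15 = 66.7% | +16.7 |
| 15 | 1/3 | (15+5)/30 = 66.7% | 5/15 = 33.3% | +33.3 |
| 27 | 2/3 | (27+2)/30 = 96.7% | 2/3 = 66.7% | +30.0 |
| 27 | 1/3 | (27+1)/30 = 93.3% | 1/3 = 33.3% | +60.0 |

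Under the first convention, each dry tract guarantees 1/30 = 3.3 points of top scores with 30 patients, or 1/20 = 5.0 points with 20.

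**The same point on the mean.** If a share b of tracts bleed with mean score s and the rest are scored 5, the reported mean is 5 − b(5 − s). For a device that stops no bleeding (s = 1) this is 5 − 4b: 4.96 at b = 1%, 3.64 at 34%, 3.00 at 50%, 1.80 at 80% and 1.00 when every tract bleeds. The values 1% and 34% are the upper liver and kidney figures in section 4.2. Those are bleeding complications, not any bleeding in the tract, so using them for b is an assumption. The distortion shrinks as tract bleeding becomes commoner.

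**The case against.** Several points on the other side are sound.

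- **No text directs a 5.** A dry tract could be left blank, and section 11.2 would treat it as missing, which causes no inflation. The case report forms are still to be developed (section 13.3) and the instructions for use are not in the documents, so a not-applicable option may appear there. This stands: inflation is likely, not certain. A score whose coding is left to the rater is still not interpretable.
- **Level 1 does not describe success.** A reader might infer that all five levels describe blood the device made stop. Only levels 2 to 5 do. What all five share is that there was blood to stop.
- **Prevention is a stated aim** (sections 4.1 and 7.1). A reader might infer that every dry tract counted as a 5 is spurious, and that d(1 − p) is the bias. The documents do not support that, because a tract dry after treatment may be the intended result. The difference in the table is a gap between two coding conventions, not a measured bias.
- **The qualifier in step 10 comes after withdrawal.** It foresees sites that do not bleed after treatment and does not show that tracts were dry beforehand. Likewise, the references to a target vessel recur in the Withdrawal Force row and look like loose wording for the treated site. Neither is relied on here.
- **The consequence is limited.** Hematoma, blood loss, ultrasound for bleeding and reintervention are captured separately, and a gauze that gains no weight does identify a site dry after withdrawal. This stands, but none of these shows whether there was bleeding to stop.

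**Conclusion.** The point holds in this form: the score is mandatory, no level fits a tract that was not bleeding, and bleeding status before activation is not recorded. Following the plan as written pools stopped and absent bleeding in the only rating labelled as device performance.

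The direction of any error is probably upward, which rests on raters tending to choose 5 for a dry tract. The size is unknown. With both inputs assumed, the gap between the two ways of coding dry tracts runs from +3.3 to +60.0 points in the table, and zero is possible.

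A reader might go further and infer that the study's bleeding outcomes are compromised. They are not, since none depends on this score. Nor does this flaw explain why a low overall bleeding rate could not be credited to the device; that is due mainly to the absence of a comparator. The point is worth correcting before enrolment because it is cheap and the missing information cannot be recovered later.

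**What to change.** 1. After step 5 and before activation, record visible bleeding through or around the guide needle (yes/no). At step 10, record bleeding during the collection period (yes/no). Both are observations only and leave the procedure unchanged.
2. Add a level to Blood Control for 'not bleeding before activation – not assessable'. Give scores 1 to 5 only to tracts bleeding before activation, and show the number not assessable beside them.
3. Report the tracts dry before activation separately, as the numbers that did and did not bleed afterwards, in a four-cell before/after table. Report gauze weight, hematoma and ultrasound for bleeding for all patients, split by status before activation.
4. State that, without a comparator, a tract dry before and after may be prevented bleeding or one that would not have bled.

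The denominator in item 2 should rest on status before treatment. Scoring every tract that bled before or after would admit initially dry tracts only when they fail. Suppose 10 tracts bleed before and all score 5, while 20 are dry before and 2 of these bleed afterwards without scoring 5. That rule gives 10/12 = 83%, although 28/30 = 93% end without bleeding. The proposed rule gives 10/10 for the score and shows 2/20 = 10% bleeding among the initially dry tracts.

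The cost is two yes/no form items, one added level and one small table. The downsides are a smaller denominator for the score, and that visible bleeding at the guide needle is an imperfect marker of bleeding along the tract.
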